**Background, Rationale and Context**

STEMI is the most severe type of heart attack and carries a 30-day mortality of nearly 8%. Reperfusion therapy is the mainstay of treatment for STEMI, either by percutaneous coronary intervention (PCI) or fibrinolysis. Delays in reperfusion are associated with negative health outcomes. Specifically, each 30-minute delay in reperfusion corresponds to a 7.5% decrease in 1-year survival. The current body of literature clearly shows that rural EMS agencies often have longer transport times, which makes the 90-minute first medical contact (FMC) to PCI time goal difficult to achieve. Approximately 16% of Americans live more than an hour from a PCI-capable facility, reinforcing the need for timely therapies in rural prehospital settings to decrease heart muscle damage (disability) and mortality. Recently, our team conducted an analysis of a large national EMS database, which showed that FMC to PCI times were longer for patients treated by rural EMS agencies even after these times were adjusted for distance to destination hospital. In addition, our preliminary data for Cherokee Tribal EMS, who serves the Eastern Band of Cherokee Indians on the Qualla Boundary and its surrounding communities, show that **none of their patients who called 9-1-1 for a STEMI received reperfusion within the AHA time goal**. The American College of Cardiology and AHA support prehospital fibrinolysis when timely PCI cannot be performed. Preliminary data from our HRSA project demonstrates the feasibility of using telehealth to guide care for a patient calling 9-1-1 for acute chest pain and suggests successful expansion to patients with acute STEMI. In Europe, telemedicine programs, which connect EMS providers with expert physicians to assist in EKG interpretation, have improved quality of care and decreased healthcare costs. In addition, these European programs have demonstrated that telehealth can improve STEMI reperfusion times in rural settings. However, STEMI telehealth programs have yet to be implemented and tested in the United States.

**Current Therapies and Unmet Medical Need Related to STEMI Care**

Rural Americans are much less likely than their urban counterparts to receive timely reperfusion. For example, since January 1, 2020 there were 37 patients with a STEMI cared for by Cherokee Tribal EMS (CTEMS), of which none (0% 0/37) received reperfusion within the American Heart Association recommended time goal. These delays in care are associated with excess mortality and high rates of

Protocol version:

Template updated 9.24.14

long-term morbidity from congestive heart failure and recurrent heart attacks. Eliminating this rural disparity is a top public health priority both nationally and locally. STEMI guidelines from the American College of Cardiology and American Heart Association (AHA) recommend reperfusion within 90 minutes of a patient's first-medical-contact (FMC) with emergency medical services (EMS). In most cases, reperfusion is accomplished with percutaneous coronary intervention (PCI; formerly known as angioplasty with stent) at tertiary care hospitals that offer this advanced capability. However, rural patients often live great distances from PCI centers and therefore have less than a 1/8th odds of timely access to PCI compared to their urban counterparts. It has been estimated that at least 16% of Americans live in rural areas over an hour drive away from a PCI-center, which makes achieving PCI within 90-minutes very difficult. For those expected to have delayed PCI, guidelines recommend administration of fibrinolytics ("clot busting medication"). However, despite these recommendations and evidence suggesting fibrinolytic administration can reduce reperfusion times, few rural EMS agencies currently administer fibrinolytics. For example, over the past four years, Cherokee Tribal EMS has never given fibrinolytics.

The major barrier to fibrinolytic use in rural EMS systems is a lack of robust medical control to ensure the safe use of this medical reperfusion treatment. Due to bleeding risk, most community emergency physicians are hesitant to order fibrinolytics without being able to evaluate the patient. Although telehealth programs are gaining popularity across the United States and successfully connecting physicians with EMS systems, including one in Wilkes County, no EMS telehealth STEMI-specific programs have been initiated in rural America to our knowledge. To overcome the main barrier to fibrinolytic use and eliminate rural disparities in STEMI care, implementation of a sustainable and scalable EMS telehealth STEMI program is needed.

Our team at the Wake Forest University School of Medicine (WFUSM), led by Drs. [name] and [name], have experience implementing a collaborative cardiovascular rural EMS telehealth project to improve rural patient access to expert cardiovascular care with Health Resources and Services Administration (HRSA) funding. This telehealth service aims to improve the care of patients who call 9-1-1 for chest pain or shortness of breath, by assisting with early risk stratification to appropriately align patient risk and resource use. Thus, we have successfully established a telehealth workflow between a rural EMS service and a team of Wake Forest physicians. At the request of Cherokee Tribal EMS we now seek to expand our existing telehealth program to this service to improve STEMI care by facilitating timely reperfusion either through PCI or thrombolysis. Patients will be considered for thrombolytics if the patient meets clinical inclusion to receive the drug, the transport time is greater than 60 minutes, and the patient is transported by CTEMS via ambulance and not by helicopter transport. (See Screening Tool, Appendix 3) This proposal, which is supported by Duke Endowment and seeks drug from Genentech, is a clinical implementation and will become the local standard of care. We aim to collect data to evaluate the impact of implementation of this EMS Telehealth STEMI program on health outcomes.

Tenecteplase (TNKase→) is a modified form of human tissue plasminogen activator (tPA) that binds to fibrin and converts plasminogen to plasmin. In vitro studies demonstrated that in the presence of fibrin, tenecteplase conversion of plasminogen to plasmin is increased relative to its conversion in the absence of fibrin. This fibrin specificity decreases systemic activation of

Protocol version:

Template updated 9.24.14

plasminogen and the resulting degradation of circulating fibrinogen compared with a molecule lacking this property, which could potentially decrease the incidence of bleeding.

Refer to the Tenecteplase Investigator's Brochure for details on nonclinical and clinical studies.

### **Approved Indication**

In the United States (US), TNKase→ (tenecteplase) is indicated to reduce the risk of death associated with acute ST elevation myocardial infarction (STEMI). In Canada, TNKase→ (tenecteplase) is indicated to reduce the mortality associated with acute myocardial infarction (AMI). Outside US and Canada, Metalyse→ (tenecteplase) is indicated in more than 90 countries for the thrombolytic treatment of AMI.

### **OVERVIEW OF CLINICAL DEVELOPMENT**

Tenecteplase has been previously developed in other indications and has been approved for the treatment of AMI.

Completed and ongoing clinical studies of tenecteplase are summarized in the Tenecteplase Investigator's Brochure.

### **Acute Myocardial Infarction Clinical Development**

Tenecteplase is indicated for use in the reduction of mortality associated with AMI and has been approved since 2000. Completed and ongoing clinical studies of tenecteplase are summarized in the Tenecteplase Investigator's Brochure.

### **Objectives**

**Objective 1:** The primary aim is to assess the impact of implementation of an EMS STEMI telehealth program on patient reperfusion times.

We seek to improve consistent achievement of the reperfusion time goals from 0% to over 75% among STEMI patients in the Qualla Boundary. In Y1 we will begin measuring the project's impact on time from FMC to reperfusion. This will be measured using electronic health records from CTEMS and WFUSM and compared to the AHA time goal of reperfusion within 90 minutes. These times are routinely and reliably documented in the health records, and we have experience abstracting them in prior clinical trials. The baseline proportion of STEMI patients meeting the AHA reperfusion time goal in Qualla Boundary is 0%. In Y2 and Y3 we anticipate achieving the AHA time goal for reperfusion in at least 75% of STEMI encounters.

**Objective 2:** Assess program uptake/adoption by Cherokee Tribal EMS paramedics.

Our goal is to establish a successful telehealth connection in 90% of CTEMS STEMI calls. Telehealth communication will be conducted using Pulsara, a HIPAA compliant platform that can connect the EMS agency to a trained Physician 24/7/365 through a video, voice call, or chat. The EMS agency will be trained on the workflow after identification of patients and when to notify a physician for a further

Protocol version:

Template updated 9.24.14

patient evaluation and medication administration support. We will review electronic health records from CTEMS and WFUSM for STEMI calls and determine if a telehealth connection was made.

## **Methods and Measures**

### **Design**

We propose a pre-post evaluation of a planned clinical implementation of an EMS STEMI telehealth program. To Improve the care for STEMI patients, a tele-health program will be implemented to provide an additional resource for Paramedics. The administration of Fibrinolitics is in the EMS formulary and considered standard of care. We will collect data from patients to assess the impact of the program and perform quality assurance.

### **Setting**

During this initial phase of this telehealth program implementation, participation will be limited to patients in Cherokee, NC who receive 9-1-1 care from Cherokee Tribal EMS, in the future this may be scaled to additional counties.

### **Subjects selection criteria**

Project participants will receive standard/usual care and will be identified for participation in electronic quality surveillance retrospectively. For patients identified for participation in this project/quality surveillance, minimal risk is expected from participation beyond that encountered in daily clinical practice, as these participants will receive standard care.

- **Inclusion Criteria**

All patients calling 9-1-1 in Qualla Boundary with possible STEMI as determined by the on scene paramedics will be included in the data.

- **Exclusion Criteria**

As this is a Quality Surveillance study, subjects will not be excluded.

- **Sample Size**

Within the Qualla Boundary we estimate 20-25 patients with EMS calls for possible STEMI will be accrued each year. Our estimated sample size that is treated with TNK is 35 total patients.

### **Interventions and Interactions**

For quality assurance data collection, participants will be identified retrospectively and data will be collected electronically using the EHR (EMS records, and WFBH medical records).

A telehealth program will be implemented to support EMS in their care of patients with STEMIs including use of fibrinolitics if indicated. Fibrinolitics are in the North Carolina Office of EMS (NCOEMS) formulary and standard of care at Wilkes EMS.

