**Request of a waiver of consent:**

- 1) *The research involves no more than minimal risk to participants.* The risk of harm or discomfort that may occur as a result of taking part in this research is not expected to be more than in daily life or from routine physical or psychological examinations or tests. Patients identified for participation in this study/quality surveillance will receive standard care. Administration of fibrinolitics is within the Scope of Practice and Protocols of Cherokee Tribal EMS. Therefore, the primary risk of participation is a breach in privacy and confidentiality.
- 2) *The waiver of informed consent will not adversely affect the rights and welfare of the participants.* The rights and welfare of participants will be protected through the use of measures to maintain the confidentiality of project information.
- 3) *The research could not practically be carried out without the waiver of informed consent.* To determine the effect of the telehealth program it must be utilized in a “real world” prehospital chest pain patient population. Performing informed consent would threaten the validity of this evaluation by introducing a significant selection bias. Furthermore, having paramedics obtain consent in the field is not practical or safe as this would prolong transport time and delay patient care, potentially leading to a worsening of clinical outcomes. In addition, ambulance transport for patients with acute chest pain is anxiety provoking. These patients are usually very concerned about having a heart attack and thus may not be in the appropriate frame of mind to ethically participate in informed consent during emergency transport.
- 4) *Participants will give verbal consent for both the conversation with the Physician and the use of the platform Pulsara.* Verbal consent for the use of the Pulsara platform will be obtained by the EMS provider. Once the physician is connected there will be a second verbal consent obtained for the conversation between the physician, EMS provider, and participant.
- 5) *Whenever appropriate, the subjects will be provided with additional information after participation.* Project results will be presented or published (if possible) in lieu of providing individual subjects additional information regarding the project.

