### **Bleeding**

The most common complication encountered during tenecteplase therapy is bleeding. This may be either superficial from punctures or damaged blood vessels or internal bleeding at any site or body cavity. Bleeding may result in life-threatening situations, permanent disability, or death.

- The incidence of intracranial hemorrhage, especially symptomatic intracranial hemorrhage (sICH), in patients with AIS is higher in alteplase-treated patients than placebo-treated patients in published studies (for detailed information, see the alteplase United States Package Insert [USPI])

The type of bleeding associated with thrombolytic therapy can be divided into two broad categories:

- Internal bleeding, involving intracranial and retroperitoneal sites, or the gastrointestinal, genitourinary, or respiratory tracts
- Superficial or surface bleeding, observed mainly at vascular puncture and access sites (e.g., venous cutdowns, arterial punctures) or sites of recent surgical intervention

Protocol version:

Template updated 9.24.14

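### The minimal-risk basis of the consent waiver is internally inconsistent: fibrinolysis is called standard care at an agency that gave none in four years, and tenecteplase has no single status in the protocol

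*Protocol*

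**What the plan says.** **On local practice.** The Design section states: "The administration of Fibrinolitics is in the EMS formulary and considered standard of care". Subjects selection criteria says that participants receive standard or usual care and derives minimal risk from that. Interventions and Interactions adds: "Fibrinolitics are in the North Carolina Office of EMS (NCOEMS) formulary and standard of care at Wilkes EMS". The Setting section, however, says that "participation will be limited to patients in Cherokee, NC who receive 9-1-1 care from Cherokee Tribal EMS". In Current Therapies and Unmet Medical Need, the protocol reports that "over the past four years, Cherokee Tribal EMS has never given fibrinolytics" and says of the proposal that it "is a clinical implementation and will become the local standard of care".

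**On risk.** Item 1 of the waiver request says that patients get standard care and that giving fibrinolytics falls within Cherokee Tribal EMS's own scope of practice and protocols. It concludes: "Therefore, the primary risk of participation is a breach in privacy and confidentiality". The section on reporting unanticipated problems names loss of confidentiality as the only expected adverse event. The Bleeding section says of tenecteplase: "Bleeding may result in life-threatening situations, permanent disability, or death".

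**On the status of the drug.** Subjects selection criteria calls the project quality surveillance from which nobody is excluded. The safety sections define adverse events against an investigational medicinal product, refer to a study drug, rely on strict eligibility criteria to protect patients, and invoke IND safety reports and IND annual reports.

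**The concern.** A review board that is asked to waive consent needs two facts: what care these patients would receive without the research, and which risks the research adds. The protocol gives conflicting answers to both. If giving tenecteplase is part of the research, a risk statement confined to privacy leaves out the most serious harm that the protocol itself describes. If it is clinical care and the research is chart review, the investigational-drug and IND language is out of place. The text then needs to say that the drug is newly introduced here, not that it is usual.

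The status of the drug also decides how harms are collected. One section says that records will not be searched for adverse events; others call for active monitoring and for reporting of all events. Under the first rule, bleeding in treated patients could go uncounted.

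**Working it through.** The protocol gives no figure to reproduce on this point. The check sets statements side by side and then sizes the change in practice.

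**1. Is fibrinolysis usual care at this agency?**
- For: the Design section (in the formulary, considered standard of care); Subjects selection criteria (standard or usual care); waiver item 1 (within this agency's scope and protocols).
- Against: no fibrinolytic given over the past four years; local standard-of-care status placed in the future (both in Current Therapies and Unmet Medical Need).
- Not relevant to this site: practice at Wilkes EMS, since Setting limits participation to Cherokee Tribal EMS.

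Formulary listing, scope of practice and agency protocols show that the drug may be given. None shows that it is given. The statement of usual care conflicts with the protocol's own account of practice.

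**2. What is the risk?**
- The waiver request names privacy as the primary risk, and the unanticipated-problems section limits expected adverse events to loss of confidentiality.
- The Bleeding section describes harm up to death. The causality guidance under Assessment of Adverse Events defines expected events as those in the package insert or Investigator's Brochure.

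The two accounts of an expected event cannot both apply. Under the second, bleeding, which the protocol calls the most common complication of tenecteplase, would be expected.

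**3. Is tenecteplase a study drug or clinical care?**
- Clinical care: Design (planned clinical implementation), Subjects selection criteria (retrospective surveillance), Informed Consent and the waiver request.
- Study drug: Adverse Events (investigational product), Methods and Timing (IND safety reports), Pregnancy (study drug), Study Close-Out (IND annual reports), Safety (eligibility criteria and safety monitoring).

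On exclusions there is a possible reconciliation: the Appendix 3 form screens patients for the drug, while nobody is excluded from the data. The protocol does not say so.

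**4. How large is the change in practice?**
Inputs: 20 to 25 possible STEMI calls a year and 35 patients treated with tenecteplase (Sample Size); about 23 months (Outcome Measures).
- Calls over 23 months: 20 × 23/12 = 38.3 and 25 × 23/12 = 47.9.
- Share treated: 35/38.3 = 91% and 35/47.9 = 73%.
- If three years is assumed instead, from the Y1 to Y3 wording of Objective 1: 60 to 75 calls, and 35/60 = 58% to 35/75 = 47%.

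On either duration the program moves the agency from no use in four years to treating roughly half or more of its possible STEMI calls.

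**The case against.** The strongest reply is that the waiver concerns chart review only. Participants are identified retrospectively, data come from electronic records, and the study evaluates a clinical implementation that proceeds regardless. On that reading privacy is the primary risk of research participation. This is a fair reading, and much of the text supports it. It is not the only one the protocol allows, because the safety sections speak of an investigational product, a study drug and IND reporting. Some of that looks like template text, but it is in force as written.

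Several stronger readings are tempting and are not supported:
- *That the waiver rests on another agency's practice.* It does not mention Wilkes EMS. It cites Cherokee Tribal EMS's own scope and protocols. The protocol also cites the state formulary, guideline support and an approved indication.
- *That the waiver claims an established local practice.* The Informed Consent section says openly that standard care will include the telehealth program after implementation in 2024. That sentence names telehealth, not a first use of fibrinolysis, and it makes care standard by virtue of the program being evaluated.
- *That none of the 37 STEMI patients since January 2020 received a fibrinolytic.* The 0/37 in the protocol counts timely reperfusion. Non-use is a separate sentence, limited to four years and without a denominator.
- *That bleeding is concealed, or that the comparison is mislabelled.* The same protocol describes bleeding at length. It also makes plain that fibrinolysis is part of the program and that reperfusion by fibrinolytic counts toward the outcome.

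**Conclusion.** The point holds as an internal inconsistency in the stated basis for minimal risk. The protocol contradicts its own premise that fibrinolysis is usual care at this agency, gives two incompatible accounts of expected harm, and does not settle whether tenecteplase is a study drug or clinical care. It matters for about 35 expected treated patients, on the protocol's own estimate. The 73% to 91% share assumes that accrual runs as stated for 23 months and that the 35 are drawn from those calls.

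A reader might infer that the waiver is invalid. The documents do not show that. It depends on whether the board accepts a separation between the clinical program and the data collection, which is the board's decision. What can be said is that the present text does not give the board a consistent basis on which to decide.

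**What to change.** 1. In Interventions and Interactions, keep the state-formulary statement and remove the clause on Wilkes EMS.
2. In Design, Subjects selection criteria, Informed Consent and the waiver request, state that prehospital fibrinolysis is permitted by this agency's protocols and supported by guidelines, was not used there in the past four years, and is introduced with the program.
3. Say that the waiver and the privacy risk concern the retrospective, record-based data collection. Disclose the tenecteplase risks as risks of the introduced program.
4. Declare one status for tenecteplase, study drug or clinical care. Reconcile to it Subjects selection criteria, the waiver request, Safety, Adverse Events, the IND reporting text, the confidentiality-only statement on expected events, and the definition of expected events. Include how adverse events are found in the records and to whom they are reported.
5. Submit the revised text to the review board, which decides on the waiver.

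The cost is a protocol amendment and a board submission. The correction to the text adds no patients or visits. If the reconciled status calls for looking for adverse events in the records, chart abstraction grows accordingly. The drawback is a less favourable risk statement.
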